8.3 Collection of adverse events

The investigator is responsible for ensuring that all staff involved in the study are familiar with the content of this section

The definitions of an AE or SAE can be found in Appendix B.

AE will be reported by the subject (or, when appropriate, by a caregiver, surrogate, or the subject's legally authorized representative).

The investigator and any designees are responsible for detecting, documenting, and recording events that meet the definition of an AE or SAE. For information on how to follow/up AEs see section 8.3.3.

8.3.1 Method of detecting AEs and SAEs

Care will be taken not to introduce bias when detecting AEs and/or SAEs. Open-ended and non-leading verbal questioning of the subject is the preferred method to inquire about AE occurrences.

8.3.2 Time period and frequency for collecting AE and SAE information

Adverse Events will be collected from Visit 2 or Visit 3 (randomisation) throughout the treatment period and including the follow-up period, Visit 13.

SAEs will be recorded from the time of signing of informed consent form.

All SAEs will be recorded and reported to the sponsor or designee within 24 hours, as indicated in Appendix B. The investigator will submit any updated SAE data to the sponsor within 24 hours of it being available.

Investigators are not obligated to actively seek AE or SAE in former study subjects. However, if the investigator learns of any SAE, including a death, at any time after a subject's last visit

and he/she considers the event to be reasonably related to the Study treatment or study participation, the investigator may notify the sponsor.

The method of recording, evaluating, and assessing causality of AE and SAE is provided in Appendix B.

8.3.3 Follow-up of AEs and SAEs

After the initial AE/SAE report, the investigator is required to proactively follow each subject at subsequent visits/contacts. All SAE/non-serious AEs will be followed until resolution, stabilization, the event is otherwise explained, or the subject is lost to follow-up.

Any AEs that are unresolved at the subject's last AE assessment in the study are followed up by the Investigator for as long as medically indicated, but without further recording in the eCRF. AstraZeneca retains the right to request additional information for any subject with ongoing AE(s)/SAE(s) at the end of the study, if judged necessary.

8.3.4 Adverse event data collection

The following variables will be collected for each AE:

- AE
- The date when the AE started and stopped
- Maximum intensity
- Whether the AE is serious or not
- Investigator causality rating against the Investigational Product(s) (yes or no)
- Action taken with regard to Investigational Product(s)
- AE causing subject's withdrawal from study (yes or no)
- Outcome.

In addition, the following variables will be collected for SAEs:

- Date AE met criteria for serious AE
- Date Investigator became aware of serious AE
- AE is serious due to
- Date of hospitalisation
- Date of discharge
- Probable cause of death
- Date of death
- Autopsy performed
- Causality assessment in relation to Study procedure(s)
- Causality assessment to other medication

8.3.5 Causality collection

The Investigator will assess causal relationship between Investigational Product and each Adverse Event, and answer 'yes' or 'no' to the question 'Do you consider that there is a reasonable possibility that the event may have been caused by the investigational product?'

For SAEs, causal relationship will also be assessed for other medication and study procedures and/or AstraZeneca (AZ) Medical device. Note that for SAEs that could be associated with any study procedure the causal relationship is implied as 'yes'.

A guide to the interpretation of the causality question is found in Appendix B.

8.3.6 Adverse events based on signs and symptoms

All AEs spontaneously reported by the subject or reported in response to the open question from the study site staff: 'Have you had any health problems since the previous visit?', or revealed by observation will be collected and recorded in the eCRF. When collecting AEs, the recording of diagnoses is preferred (when possible) to recording a list of signs and symptoms. However, if a diagnosis is known and there are other signs or symptoms that are not generally part of the diagnosis, the diagnosis and each sign or symptom will be recorded separately.

8.3.7 Adverse events based on examinations and tests

The results from the Clinical Study Protocol mandated laboratory tests and vital signs will be summarised in the CSR. Deterioration as compared to baseline in protocol-mandated laboratory values, vital signs and physical examinations should therefore only be reported as AEs if they fulfil any of the SAE criteria or are the reason for discontinuation of treatment with the investigational product.

If deterioration in a laboratory value/vital sign is associated with clinical signs and symptoms, the sign or symptom will be reported as an AE and the associated laboratory result/vital sign will be considered as additional information. Wherever possible the reporting Investigator uses the clinical, rather than the laboratory term (e.g., anaemia versus low hemoglobin value). In the absence of clinical signs or symptoms, clinically relevant deteriorations in non-mandated parameters should be reported as AE(s).

Any new or aggravated clinically relevant abnormal medical finding at a physical examination as compared with the baseline assessment will be reported as an AE.

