8.2.2 Physical examinations

A complete physical examination will be performed and include an assessment of the following: general appearance, respiratory, cardiovascular, abdomen, skin, head and neck (including ears, eyes, nose and throat), lymph nodes, thyroid, musculo-skeletal (including spine and extremities) and neurological systems.

Targeted examinations (evaluation of selective body systems at the judgement of the physician or qualified designee based on subject presentation) are sufficient for the remaining time points after the screening.

Physical examination will be performed at timelines as specified in the SoA, Investigators should pay special attention to clinical signs related to previous serious illnesses, new or worsening abnormalities may qualify as adverse events, see Sections 8.3.6 and 8.3.7 for details. Height will be measured at screening.

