9.4.2 Safety analyses

Safety analysis will be based on Safety set.

Adverse events will be coded using the Medical Dictionary for Regulatory Activities (MedDRA). The type, incidence, severity and relationship to investigational product of each AE will be summarized by MedDRA System Organ Class and Preferred Term, using number and percentage of patients with certain events. AEs with onset on or after first day of IP will be mainly evaluated. Other safety variables such as 24-hour ABPM, vital signs, ECG and safety laboratory tests will be summarized descriptively by treatment and visit, as appropriate.

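### Section 8.3.7 gives two incompatible AE-reporting rules for a clinically relevant, non-serious physical-examination finding that does not stop treatment

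*Protocol*

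**What the plan says.** All of the conflicting text is in Protocol Section 8.3.7.

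- The section opens with a premise: "The results from the Clinical Study Protocol mandated laboratory tests and vital signs will be summarised in the CSR".
- From that premise it draws a restriction: "Deterioration as compared to baseline in protocol-mandated laboratory values, vital signs and physical examinations should therefore only be reported as AEs". The same sentence then names the two grounds on which reporting is allowed: "if they fulfil any of the SAE criteria or are the reason for discontinuation of treatment with the investigational product".
- It ends with a rule specific to examinations: "Any new or aggravated clinically relevant abnormal medical finding at a physical examination as compared with the baseline assessment will be reported as an AE".

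Section 8.2.2 sends the reader back to the same place: "new or worsening abnormalities may qualify as adverse events, see Sections 8.3.6 and 8.3.7 for details".

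Section 9.4.2 says that AEs will be tabulated as number and percentage of patients. For the rest it says: "Other safety variables such as 24-hour ABPM, vital signs, ECG and safety laboratory tests will be summarized descriptively by treatment and visit". Table 5 in Section 3 lists AEs among the measures for the primary safety objective.

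**The concern.** A site that finds a new, clinically relevant but non-serious abnormality at a scheduled examination, in a subject who continues treatment, cannot comply with both sentences. Whichever it follows, it breaches the other.

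The reason given for the restriction also fails to cover examinations. Restricting AE reporting is sensible where the underlying values are summarised anyway, and the premise says so for laboratory tests and vital signs. It does not mention physical examinations, and neither do the examples in Section 9.4.2. Under the restrictive rule, such a finding may therefore appear in no summary that the protocol names, unless it is picked up under Section 8.3.6.

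What is at stake is how uniformly part of the primary safety endpoint is collected. The SAP cannot repair this, because no analysis recovers an AE that a site was told not to record.

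**Working it through.** No stated figure needs reproducing. The check is a comparison of text, plus one line of arithmetic for scale.

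**Step 1: do both rules apply to the same examinations?** The restriction covers protocol-mandated physical examinations. Section 8.2.2 makes them mandated: "Physical examination will be performed at timelines as specified in the SoA". Table 2 schedules targeted examinations on Days 1, 6, 13, 20, 34 and 48 and at follow-up, which is seven visits. The last sentence of 8.3.7 covers findings at any physical examination. Both rules therefore reach all seven.

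**Step 2: apply each rule to each kind of clinically relevant new or aggravated finding.**

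| Finding | Opening paragraph | Last sentence |
|---|---|---|
| Meets an SAE criterion | Report | Report |
| Non-serious, and the reason for stopping treatment | Report | Report |
| Non-serious, treatment continues | Do not report | Report |

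The rules agree in two rows and conflict in the third.

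**Step 3: can wording separate the rules?**

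- *Deterioration versus new finding.* A new abnormality compared with baseline is a deterioration, and an aggravated one plainly is. The two terms overlap.
- *Clinical relevance.* This limits the last sentence, but the restriction makes no exception for clinically relevant findings.
- *Exception.* The last sentence is not worded as an exception. If it were one, the mention of examinations in the opening paragraph would have almost no effect.
- *Cross-reference.* Section 8.2.2 says only that abnormalities may qualify as AEs, and points back to 8.3.6 and 8.3.7.

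**Step 4: which phrase is out of place?** The premise of the restriction names laboratory tests and vital signs. The second paragraph of 8.3.7 again speaks only of a laboratory value or vital sign. Appendix B 1 counts unfavourable and unintended signs as possible AEs. The mention of physical examinations in the restrictive sentence is the one element that does not fit the rest.

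**Step 5: scale.** The synopsis gives 15 subjects per arm. If a subject's only event of a given type is a finding in the third row, the choice of rule moves that arm's incidence by 1/15 = 6.7 percentage points. The protocol gives no expected number of such findings, so the total effect cannot be calculated.

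**The case against.** The best case on the other side has four parts.

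**A workable reading exists.** The last sentence is the only one devoted to examinations, it is limited to clinically relevant findings, and it is mandatory, whereas the opening paragraph says only what should be done. Reading the specific over the general would make it the operative rule. That is reasonable, but the text does not say so, and different sites can read it differently.

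**Findings are not necessarily lost.** A reader might infer that, under the restrictive rule, non-serious examination findings would be reported nowhere. The protocol does not support that. Section 8.3.6 collects AEs revealed by observation with no seriousness condition, Appendix B 1 defines AEs broadly, and the list in Section 9.4.2 is given as examples. This part stands. It also adds a third possible route, which does not make reporting more uniform.

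**The affected set is narrow.** After screening, examinations are targeted by how the subject presents, so many will follow a complaint already collected under 8.3.6. The safety concerns named in Section 4.2.2.1 (gastrointestinal events, heart rate, blood pressure and QTcF) come mainly from symptom reports, the diary, vital signs, ambulatory monitoring and ECG. This stands and limits the consequence.

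**No distortion between arms is shown.** A reader might infer that inconsistent sites would create false differences between doses. Allocation is randomised 1:1:1:1, evaluators are intended to be blinded, and a site's reading applies to its subjects whatever their arm. The expected result is under-counting and noise. Chance imbalance of arms within sites is possible but cannot be estimated. Nor does arm size show that one or two reclassified findings would be visible. Taking 3, 4 and 5 subjects out of 15 purely as assumed counts, the exact 95% intervals are 4.3–48.1%, 7.8–55.1% and 11.8–61.6%. They overlap heavily, so sampling error is larger than the reclassification.

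**Conclusion.** The contradiction is certain and lies within one section of the current text. It affects one class of event: clinically relevant, non-serious physical-examination findings in subjects who continue treatment. For that class, sites may record AEs inconsistently, and the restrictive reading may leave findings out of every summary the protocol names unless 8.3.6 catches them.

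The consequence is modest. One subject is 6.7 percentage points of an arm, but the number of such findings is unknown. The overall effect is probably small, in the direction of under-ascertainment and added noise, with no demonstrated bias between arms. This assumes that evaluators stay blinded and that each site applies its reading to all its subjects.

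The point still merits a change. Safety is judged descriptively from these counts (Section 9.1), the fault lies in collection rather than analysis, and the correction is simple.

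**What to change.** Reconcile the two sentences of Section 8.3.7 into one reporting rule:

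- Remove physical examinations from the restrictive sentence, so that it covers only protocol-mandated laboratory values and vital signs, the two categories its own premise names.
- Keep the last sentence unchanged as the sole rule for physical-examination findings.
- Send the clarification to all sites at the same time.

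The cost is one deleted phrase, a site communication and a few more non-serious AEs.

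The further cost is timing. The version history dates version 8.0 to 12 June 2019, and the synopsis estimates first enrolment in July 2018 and last completion in January 2020. A clarification issued while the trial is running could shift ascertainment part-way through, which is itself an inconsistency. To contain this, document the date of the clarification and ask sites to check examination findings already in source against the single rule.

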8.3.8 Hy's law

Cases where a subject shows elevations in liver biochemistry may require further evaluation and occurrences of AST or ALT $\geq 3xULN$ together with total bilirubin $\geq 2xULN$ may need to

be reported as SAEs. Please refer to Appendix E for further instruction in the case of increases in liver biochemistry and evaluation of Hy's Law

8.4 Safety reporting and medical management

8.4.1 Reporting of serious adverse events

All SAEs have to be reported, whether or not considered causally related to the investigational product, or to the study procedure(s). All SAEs will be recorded in the eCRF.

If any SAE occurs in the course of the study, then Investigators or other site personnel inform the appropriate AstraZeneca representatives within one day i.e., immediately but **no later than 24 hours** of when he or she becomes aware of it.

The designated AstraZeneca representative works with the Investigator to ensure that all the necessary information is provided to the AstraZeneca Patient Safety data entry site **within 1 calendar day** of initial receipt for fatal and life-threatening events **and within 5 calendar days** of initial receipt for all other SAEs.

For fatal or life-threatening adverse events where important or relevant information is missing, active follow-up is undertaken immediately. Investigators or other site personnel inform AstraZeneca representatives of any follow-up information on a previously reported SAE within one calendar day i.e., immediately but **no later than 24 hours** of when he or she becomes aware of it.

Once the Investigators or other site personnel indicate an AE is serious in the EDC system, an automated email alert is sent to the designated AstraZeneca representative.

If the EDC system is not available, then the Investigator or other study site staff reports an SAE to the appropriate AstraZeneca representative by telephone.

The AstraZeneca representative will advise the Investigator/study site staff how to proceed.

For further guidance on the definition of a SAE, see Appendix B of the Clinical Study Protocol.

8.4.2 Pregnancy

All pregnancies and outcomes of pregnancy should be reported to AstraZeneca except for:

- If the pregnancy is discovered before the study subject has received any study drug
- If a pregnancy is reported, the investigator should inform the sponsor within 24 hours of learning of the pregnancy.
- If the investigator become aware of a pregnancy in the partner of a male study subject who has received investigational product, then the investigator or other site personnel will

inform the appropriate sponsor representatives within 24 hours of learning of the pregnancy.

- Abnormal pregnancy outcomes (e.g., spontaneous abortion, foetal death, stillbirth, congenital anomalies, ectopic pregnancy) are considered SAEs.

8.4.2.1 Maternal exposure

If a subject becomes pregnant during the course of the study, investigational product should be discontinued immediately.

Pregnancy itself is not regarded as an adverse event unless there is a suspicion that the investigational product under study may have interfered with the effectiveness of a contraceptive medication. Congenital abnormalities/birth defects and spontaneous miscarriages should be reported and handled as SAEs. Elective abortions without complications should not be handled as AEs. The outcome of all pregnancies (spontaneous miscarriage, elective termination, ectopic pregnancy, normal birth or congenital abnormality) should be followed up and documented even if the subject was discontinued from the study.

If any pregnancy occurs in the course of the study, then the Investigator or other site personnel informs the appropriate AstraZeneca representatives within 1 day i.e., immediately but **no later than 24 hours** of when he or she becomes aware of it.

The designated AstraZeneca representative works with the Investigator to ensure that all relevant information is provided to the AstraZeneca Patient Safety data entry site within 1 or 5 calendar days for SAEs (see Section 8.4.1) and within 30 days for all other pregnancies.

The same timelines apply when outcome information is available.

The PREGREP module in the eCRF is used to report the pregnancy.

8.4.3 Overdose

For this study, any dose of MEDI0382 greater than the dose at > 300 µg will be considered an overdose. The investigator should report an overdose to the sponsor when the subject injects more than once a day.

No specific treatment is recommended for an overdose.

- An overdose with associated AEs is recorded as the AE diagnosis/symptoms on the relevant AE modules in the eCRF and on the Overdose eCRF module.
- An overdose without associated symptoms is only reported on the Overdose eCRF module

If an overdose on an AstraZeneca study drug occurs in the course of the study, then the Investigator or other site personnel inform appropriate AstraZeneca representatives immediately, or **no later than 24 hours** of when he or she becomes aware of it.

The designated AstraZeneca representative works with the Investigator to ensure that all relevant information is provided to the AstraZeneca Patient Safety data entry site.

- For overdoses associated with a SAE, the standard reporting timelines apply, see Section 8.3.2. For other overdoses, reporting must occur within 30 days.

8.4.4 Medical device incidents (including malfunctions)

Medical devices are being provided for use in this study. In order to fulfil regulatory reporting obligations worldwide, the investigator is responsible for the detection and documentation of events meeting the definitions of incident or malfunction that occur during the study with such devices.

The definition of a Medical Device Incident can be found in Appendix F

NOTE: Incidents fulfilling the definition of an AE/SAE will also follow the processes outlined in Section 8.3 and Appendix B.

8.4.4.1 Time period for detecting medical device incidents

- Medical device incidents or malfunctions of the device that result in an incident will be detected, documented, and reported during all periods of the study in which the medical device is used.
- If the investigator learns of any incident at any time after a subject has been discharged from the study, and such incident is considered reasonably related to a medical device provided for the study, the investigator will promptly notify the sponsor.

The method of documenting Medical Device Incidents is provided in Appendix F.

8.4.4.2 Follow-up of medical device incidents

- All medical device incidents involving an AE will be followed and reported in the same manner as other AEs (see Section 8.3.3). This applies to all subjects, including those who discontinue Study treatment.
- The investigator is responsible for ensuring that follow-up includes any supplemental investigations as indicated to elucidate the nature and/or causality of the incident.
- New or updated information will be recorded on the originally completed form with all changes signed and dated by the investigator.

8.4.4.3 Reporting of medical device incidents to sponsor

- Medical device incidents will be reported to the sponsor within 24 hours after the investigator determines that the event meets the protocol definition of a medical device incident.
- Medical Device Incident will be reported via eCRF. If eCRF is unavailable, then e-mail communication should be utilized.
- The same individual will be the contact for the receipt of medical device reports and SAE.
- If an investigational medical device is used, the Study Representative will send the SAE report to AZ data entry site within **one calendar day**.

8.4.4.4 Regulatory reporting requirements for medical device incidents

- The investigator will promptly report all incidents occurring with any medical device provided for use in the study in order for the sponsor to fulfil the legal responsibility to notify appropriate regulatory authorities and other entities about certain safety information relating to medical devices being used in clinical studies.
- The investigator, or responsible person according to local requirements (e.g., the head of the medical institution), will comply with the applicable local regulatory requirements relating to the reporting of incidents to the IRB/IEC.

